##### **Question 6: How often do you have good days (with little chest trouble)?**

None 93.3  
A few 76.6  
Most are good 38.5  
Every day 0.0

##### **Question 7: If you have a wheeze, is it worse in the morning?**

No 0.0  
Yes 62.0

## **Part 2**

### **Question 8: How would you describe your chest condition?**

The most important problem I have 82.9

Causes me a few problems 34.6

Causes no problem 0.0

### **Question 9: Questions about what activities usually make you feel breathless.**

Getting washed or dressed 82.8

Walking around the home 80.2

Walking outside on the level 81.4

Walking up a flight of stairs 76.1

Walking up hills 75.1

### **Question 10: More questions about your cough and breathlessness.**

My cough hurts 81.1

My cough makes me tired 79.1

I get breathless when I talk 84.5

I get breathless when I bend over 76.8

My cough or breathing disturbs my sleep 87.9

I get exhausted easily 84.0

### **Question 11: Questions about other effects your chest trouble may have on you.**

My cough or breathing is embarrassing in public 74.1

My chest trouble is a nuisance to my family, friends or neighbors 79.1

I get afraid or panic when I cannot get my breath 87.7

I feel that I am not in control of my chest problem 90.1

I have become frail or an invalid because of my chest 89.9

Exercise is not safe for me 75.7

Everything seems too much of an effort 84.5

### **Question 12: Questions about how activities may be affected by your breathing.**

I take a long time to get washed or dressed 74.2

I cannot take a bath or shower, or I take a long time 81.0

I walk more slowly than other people, or I stop for rests 71.7

Jobs such as housework take a long time, or I have to stop for rests 70.6

If I walk up one flight of stairs, I have to go slowly or stop 71.6

If I hurry or walk fast, I have to stop or slow down 72.3

My breathing makes it difficult to do things such as walk up hills, carry things up stairs, light gardening such as weeding, dance, play bowls or play golf 74.5

My breathing makes it difficult to do things such as carry heavy loads, dig the garden or shovel snow, jog or walk at 5 miles per hour, play tennis or swim 71.4

### **Question 13: We would like to know how your chest trouble usually affects your daily life.**

I cannot play sports or games 64.8

I cannot go out for entertainment or recreation 79.8

I cannot go out of the house to do the shopping 81.0

I cannot do housework 79.1

I cannot move far from my bed or chair 94.0

**Question 14: Tick the statement which you think best describes how your chest affects you.**

- It does not stop me doing anything I would like to do 0.0
- It stops me doing one or two things I would like to do 42.0
- It stops me doing most of the things I would like to do 84.2
- It stops me doing everything I would like to do 96.7

The symptoms component consists of all the questions in Part 1. The activity component consists of questions 9 and 12 in Part 2 of the questionnaire. The impact component consists of questions 8, 10, 11, 13, 14 in Part 2 of the questionnaire

The score for each component is calculated separately by dividing the summed weights by the maximum possible weight for that component and expressing the result as a percentage:

$$\text{Score} = 100 \times \frac{\text{Summed weights from all positive items in that component}}{\text{Sum of weights for all items in that component}}$$

The total score is calculated in similar way:

$$\text{Score} = 100 \times \frac{\text{Summed weights from all positive items in the questionnaire}}{\text{Sum of weights for all items in the questionnaire}}$$

The 0% and 100% represent the best and worst possible health status, respectively.

Missing items will be imputed using the rules described in Section 3.1.5 in this SAP.

The SGRQ-C total score and component scores, as well as the absolute and percent change from baseline at Week 14, end of treatment period and other study visits will be summarized by treatment group using descriptive statistics.

### **3.3.2.4 Change from Baseline in Post-Bronchodilator FEV1 at Week 13**

The post-bronchodilator FEV1, as well as the absolute and percent changes from baseline will be summarized by treatment group and study visit using descriptive statistics. The absolute and percent changes from baseline to the end of treatment period will also be summarized.

### **3.3.3 Analysis of Exploratory Endpoints**

#### **3.3.3.1 Change from Baseline in Sputum Mucins (Total, MUC5AC, and MUC5B)**

The sputum mucins results, absolute change and percent change from baseline will be summarized by treatment group and study visit using descriptive statistics.

### **3.3.3.2 Change from Baseline in ENaC (mRNA) Levels from Bronchial Brushings at Week 13**

Due to the limited post-treatment bronchial brushing samples, the data will only be provided in the data listing.

### **3.3.3.3 Change from Baseline in Inflammatory Biomarkers from BAL at Week 13**

Due to the limited post-treatment BAL samples, the data will only be provided in the data listing.

### **3.3.3.4 Change from Baseline in Inflammatory Biomarkers from Sputum**

The results, absolute change and percent change from baseline in the inflammatory biomarkers will be summarized by treatment group and study visit using descriptive statistics.

### **3.3.3.5 Change from Baseline in FRC and RV at Week 14**

The FRC and RV, as well as the absolute change and percent change from baseline will be summarized by treatment group and study visit using descriptive statistics.

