**Analytical visits:**

Efficacy/PD data including spirometry, CAT, SGRQ, sputum mucins, ENaC mRNA, inflammatory biomarkers, during the treatment period will be mapped to analysis visit as specified in the table (

**Efficacy/PD Measure Visit Windows**) below. The intent of these visit windows is not to align with those prescribed for visit scheduling in the clinical study protocol but, rather, based on the protocol-defined target study day, to delineate mutually exclusive windows so that all assessments proximal to a particular study week can be integrated to best represent the patient's status during that period of the study.

If a patient discontinued early from the treatment period but attended applicable landmark visits to collect assessments, then those assessments collected within 14 days after the last dose of Study Drug will be included as long as they are within the defined analysis windows.

The unscheduled visits will also be included if they are collected within 14 days after the last dose of Study Drug and within the defined analysis windows.

If there are multiple assessments within a visit window, the visit nearest the scheduled date will be used unless 2 visits are equally near, in which case the average will be used for continuous results, and the worst will be used for categorical results.

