**Efficacy/PD Measure Visit Windows**

Measure	Mapped Visit (Week)	Target Day	Study Day Window
Spirometry assessments	1 – 1 hour post dose	1	1
	1 – 2 hours post dose	1	1
	3	15	2-22
	5	29	23 to 36
	7	43	37 to 50
	9	57	51 to 71
	9 – 1 hour post dose	57	51 to 71
	9 – 2 hours post dose	57	51 to 71
	13	85	72 to 88
	14	92	89 to 99
CAT and SGRQ	5	29	2 to 43
	9	57	44 to 74
	14	92	75 to 99
EXACT	2	8	2-8
	3-14	15-99	(Week-1)*7-5 to (Week-1)*7+1
Sputum mucins	5	29	23 to 36

Measure	Mapped Visit (Week)	Target Day	Study Day Window
	7	43	37 to 64
	13	85	65 to 88
	14	92	89 to 99
Plethysmography assessments,	14	92	75 to 99

Data collected under visit labels containing Weeks 18, 24, Days 120 or 162 will not be mapped to analysis week.

Visits after Week 14 are part of the post-treatment assessment period. The efficacy and PD data during the post-treatment period will be summarized using the visit labels provided in the data.

Other data will be summarized using the visit labels provided in the data. Multiple results with the same visit label will be averaged. Results with visit labels as “Unscheduled” will not be included in the by-visit summary tables and figures, but will be included in determining baseline, and in the laboratory abnormality summaries and shift analyses.

All data will be presented in data listings.

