### **3.3 Efficacy Analyses**

All efficacy analyses will be performed on the FAS. Due to the fact that study treatment terminated after only 60 patients have been randomized, 59 patients have been dosed, and 10 patients have completed the Week 14, all analyses will be descriptive. The model-based analyses described in the protocol will not be conducted.

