#### **3.3.1 Change from Baseline in FEV1 at the Primary Time Point**

The FEV1 and other spirometry assessments, as well as change and percent change from baseline to the primary time point, end of treatment period, and other study visits will be summarized by treatment group using descriptive statistics.

At each time point, 3 technically acceptable measurements will be made and recorded. The best readings from each time point for each assessment will be used for analysis.

In addition to the descriptive summary, the proportion of patients who have a greater than 20% reduction in FEV1 post treatment and the proportion of doses that resulted in a greater than 20% reduction in FEV1 will be tabulated by treatment group.

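### FRC and RV have one analysis window (Days 75 to 99) and no end-of-treatment summary, so lung volumes measured at early termination before Day 75 enter no post-baseline summary table

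*Combined protocol and SAP*

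**What the plan says.** - **Summary rule.** SAP 3.3.3.5: "The FRC and RV, as well as the absolute change and percent change from baseline will be summarized by treatment group and study visit". The section title ties the analysis to Week 14, and no end-of-treatment summary is mentioned.
- **Timing.** Protocol 8.3.4 and the Appendix A schedule place plethysmography at Screening and at Day 92. The Day 92 column is also the Early Termination column.
- **Window.** The SAP 3.1.1 table gives lung volumes one row: "Plethysmography assessments, 14 92 75 to 99" (mapped week, target day, day range).
- **Early discontinuers.** Under SAP 3.1.1, values taken within 14 days of the last dose "will be included as long as they are within the defined analysis windows".
- **Termination.** SAP 1.1 records that treatment was stopped on 29 April 2021 with 59 patients dosed, and that patients then on treatment go on to the early termination visit. SAP 3.3 adds that "10 patients have completed the Week 14" and makes all analyses descriptive. The SAP is dated 26 August 2021.
- **Contrast.** SAP 3.1.1 defines an end-of-treatment assessment (the latest value no more than 14 days past the final dose). Section 3.3.1 uses it for spirometry: "change and percent change from baseline to the primary time point, end of treatment period, and other study visits will be summarized". Sections 3.3.2.1 to 3.3.2.4 use it for E-RS, CAT, SGRQ-C and post-bronchodilator FEV1.

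**The concern.** Patients whose treatment was stopped early can have lung volumes measured on any study day. With one window that opens on Day 75, an earlier value has no row to enter. The SAP was written after termination, and it has a device that handles this situation, but it does not apply that device to FRC and RV.

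Change in lung volumes is still a stated exploratory objective and endpoint. The neighbouring mechanism readouts are already reduced: HRCT was not collected, and BAL and bronchial-brushing results are listing-only. What is at stake is whether the FRC/RV table uses all the on-treatment measurements or only those inside the Week 14 window.

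**Working it through.** The plan states no figure on this point, so there is none to reproduce. The check uses the SAP 3.1.1 windows, the weekly dosing days (1, 8, ..., 85; 13 doses) and the 14-day rule.

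**Step 1. Which of Study Days 2 to 99 have a window?**

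| Measure | Windows | Days with no window |
|---|---|---|
| Spirometry | 2-22, 23-36, 37-50, 51-71, 72-88, 89-99 | none |
| CAT, SGRQ | 2-43, 44-74, 75-99 | none |
| Sputum mucins | 23-36, 37-64, 65-88, 89-99 | 2-22 (21 days) |
| Plethysmography | 75-99 | 2-74 (73 days) |

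Spirometry, CAT and SGRQ have no gap, yet they receive an end-of-treatment summary. Lung volumes have the largest gap and do not.

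**Step 2. Can an early termination visit reach the window?** For a last dose on day d, the days allowed are d+1 to d+14. The number that fall in Days 75 to 99 is max(0, min(d+14, 99) - max(d+1, 75) + 1).

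| Last dose (nominal day) | Allowed days | Days inside window |
|---|---|---|
| 1 to 57 (doses 1-9) | up to Day 71 at the latest | 0 of 14 |
| 64 (dose 10) | 65-78 | 4 of 14 |
| 71 (dose 11) | 72-85 | 11 of 14 |
| 78 (dose 12) | 79-92 | 14 of 14 |
| 85 (dose 13) | 86-99 | 14 of 14 |

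The Day 57 result survives the visit window of plus or minus 3 days in Appendix A: 60 + 14 = 74, still short of Day 75.

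If the visit falls 7 days after the last dose (an assumption, mirroring Day 85 to Day 92), it reaches Day 75 only when d is at least 68. Every last dose up to Day 64, which is 10 of the 13 dosing days, then gives an untabulated value.

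**Step 3. How many patients?** 59 dosed - 10 who completed Week 14 = 49, and 49/59 = 83%. This is a ceiling. It would require all 49 to have had plethysmography, and all before Day 75. The documents give neither exposure at termination nor the dates of these tests, so the range is 0 to 49.

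**The case against.** **It may be deliberate.** The end-of-treatment summary follows endpoint tier: every primary and secondary efficacy measure has it and no exploratory one does. Declining to pool lung volumes taken after very different numbers of doses is defensible. But the SAP never states that rationale. Where it intends listing-only reporting (3.3.3.2 and 3.3.3.3), it says so and gives a reason. For FRC and RV it promises a summary by treatment group.

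**Nothing is hidden.** This stands. SAP 3.1.1 puts all data in listings and SAP 3.2 tabulates baseline FRC and RV. The gap is confined to post-baseline summary tables.

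**Visit labels might rescue the values.** SAP 3.1.1 uses visit labels for visits after Week 14 and for other data. Plethysmography has its own window row, so that rule does not clearly apply. If it did, a value from, say, Day 30 could be reported as Week 14, which would also need correcting.

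**Stronger readings a reader might infer, which the documents do not support:**
- *That sputum mucins are lost in the same way.* Their windows run unbroken from Day 23 to Day 99. Later early termination samples are tabulated if taken within 14 days of the last dose. Their spread over several week rows is ordinary time-matched reporting.
- *That sputum inflammatory biomarkers are summarised only by mapped visit.* SAP 3.1.1 lists inflammatory biomarkers as mapped, but the window table has no row for them. Section 3.3.3.4 says only: "The results, absolute change and percent change from baseline in the inflammatory biomarkers will be summarized by treatment group and study visit using descriptive statistics". Their placement is undefined, and summary by visit label is possible.
- *That most on-treatment lung volumes are left out, with standard errors about 2.4 times larger.* sqrt(59/10) = 2.43 assumes that all 49 were measured before Day 75, that every one would be recovered by an end-of-treatment row, and that the standard deviation is equal across treatment durations. None of this is documented.

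**Conclusion.** The point holds for FRC and RV. As the SAP is written, lung volumes taken at early termination on Days 2 to 74 have no place in any post-baseline summary table. For a last dose on or before Day 57 this is certain for any visit within the 14-day limit; for a last dose on Day 64 or 71 it depends on the visit day.

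The size is unknown: 0 to at most 49 of 59 dosed patients. These are exploratory endpoints in a terminated study with descriptive reporting and no model-based analyses. The loss is therefore of information and precision, and no primary or secondary result changes. The conclusion rests on reading the plethysmography row as governing these values, which is the natural reading of the table. The sputum measures are a secondary matter: a 21-day gap for mucins and a missing window row for biomarkers.

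**What to change.** In SAP 3.3.3.5, add that absolute and percent change in FRC and RV from baseline to the end of treatment period, as defined in SAP 3.1.1, will be summarised by treatment group. Show the number of doses received beside it and keep the Week 14 row.

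The same sentence may be added to 3.3.3.1 for mucins and to 3.3.3.4 for sputum biomarkers, but this is optional.

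The cost is one sentence and one extra table row for FRC/RV, using an existing definition and no new data. There are two limits. The row mixes treatment durations, as the SAP already accepts for FEV1, E-RS, CAT, SGRQ-C and post-bronchodilator FEV1; showing doses received makes this visible. Tests done more than 14 days after the last dose would still be left out, and protocol 8.8 treats two weeks as an ideal, not a requirement.

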### **3.3.3.6 Change from Baseline in Regional Lung Volumes as measured by HRCT at Week 14**

Since no patients have been enrolled in the HRCT subgroup at the time of treatment termination and the HRCT data are not collected. The data analysis will not be conducted.

## **3.4 Safety Analyses**

Safety analyses will be performed on the safety population.

### **3.4.1 Exposure**

Treatment duration, number of doses, amount of Study Drug and number of patients with dose interruption will be summarized by Part and treatment group.

The treatment duration (days) for each patient is defined as last dose date - first dose date +1.

### **3.4.2 Adverse Events**

An adverse event will be regarded as treatment emergent if it is present prior to receiving the first dose of study drug and subsequently worsens, or is not present prior to receiving the first dose of study drug but subsequently appears.

In addition, if the severity of an AE changes during the study, a separate AE will be recorded for each severity on the AE CRF. The “first” and “second” AE records will be identified based on the AE start date. AE start date of the second record will be the AE stop date of first record. These linked events should be compared pairwise. Consider the following two cases,

where the AE severity (mild/moderate/severe) and seriousness (Yes/No) between the two records in a pair are compared.

Case 1: The first AE record in the pair occurs before the first dosing, and the second AE record occurs after the first dosing.

If the AE severity or seriousness of the second record is worse than that of the first record, then only the second AE is deemed as a TEAE. Otherwise, neither record is considered as TEAE.

Case 2: Both AE records in the pair occur after first dosing.

The worst AE is considered as a TEAE.

The most conservative approach will be used to determine if the event occurs after the treatment. For example, if the onset date or resolution date of an AE is prior to the first study treatment date, it will be considered to have occurred prior to the study period. If the onset or resolution date of an AE is a partial date with only month or year available or complete missing, then the event is assumed to be within the study period unless the year is prior to the year of the first study treatment date, or if in the same year, the month is prior to the month of the first study treatment date.

The incidence of AEs will be summarized by Medical Dictionary for Regulatory Activities (MedDRA) preferred term and system organ class for:

- Any treatment emergent adverse events
- Related treatment emergent adverse events. Related is defined as “Related”, “Possible”, or missing relationship to study drug
- Any treatment emergent adverse events by severity. At each level of patient summarization, a patient is classified according to the highest severity if the patient reported one or more events. Adverse events with missing severity will categorized as “Missing” for this summary
- Related treatment emergent adverse events by severity
- Serious treatment emergent adverse events
- Serious and related treatment emergent adverse events

AEs that lead to investigational drug discontinuation will be listed. Non-treatment emergent adverse event will be flagged in the data listing.

### **3.4.3      Laboratory Measurements**

The list of safety lab analytes collected throughout the study is provided in protocol Appendix B.

All lab data collected will be presented in subject listings.

Results from chemistry, hematology, complements, and coagulation panels as well as the change and percent change from baseline will be summarized by treatment group and study visit using descriptive statistics.

For ALT and AST, the number and percent of subjects falling in each of the following categories based on the confirmed results will be tabulated by treatment group

- ALT/AST > 3 x ULN, which is confirmed
- ALT/AST > 5 x ULN, which is confirmed

For platelet, the number and percentage of subjects falling in each of the following categories based on the confirmed results will be tabulated by treatment group for 100,000/mm^3 to <140,000/mm^3 and <100,000/mm^3.

A confirmed value is based on a consecutive lab value within 7 days. If that value is in the same or worse category the initial value is confirmed. If the consecutive value is in a better category, then the initial value is confirmed using the consecutive value category. If there is no retest within 7 days, then the initial value is presumed confirmed. If there are multiple results on the same day, then the worst value will be utilized in the analysis.

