#### **10.6.2. Safety Analysis**

Treatment duration and amount of Study Drug (ION-827359 or placebo) received will be summarized by treatment group.

All treatment emergent AEs, all treatment emergent AEs potentially related to Study Drug, all treatment emergent serious AEs, and all treatment emergent serious AEs potentially related to

Study Drug (ION-827359 or placebo) will be summarized for each treatment group using the Medical Dictionary for Regulatory Activities (MedDRA™) coding system, by system organ class, preferred term, relationship to Study Drug, and severity. Narratives of deaths, SAEs, including early withdrawals from treatment and from study due to AE, will also be provided.

Laboratory tests to ensure subject safety including chemistry panel, complete blood count with differential, coagulation panel, etc., will be summarized by study visits for each treatment group. These safety variables will also be presented as change and percent change from Baseline over time after Study Drug administration, as appropriate.

Vital sign and ECG measures will be tabulated by treatment group. In addition, the number of patients who experience abnormalities in clinical laboratory evaluations will be summarized by treatment group.

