### **Baseline definition**

Baseline E-RS total and subscale scores are defined as the average of daily scores collected on Day 1 and within 6 days prior to Day 1.

Baseline liver chemistry parameters (ALT, AST, and total, direct and indirect bilirubin, alkaline phosphatase) are defined as the average of the non-missing values at Screening and Day 1 pre-dose, and any values in between.

Baseline ECG assessments are defined as the last triplicate prior to the first Study Drug administration. For numeric results, the baseline is the average of the triplicate. For character results, baseline is the worst result of the triplicate.

Baseline for other assessments is defined as the last non-missing measurement prior to the first Study Drug administration.

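### Minor: SAP 3.4.3 counts patients only for ALT/AST and platelets, so potassium, creatinine and urine protein at stop levels have no count table; separately, the creatinine units in protocol 8.6.2 disagree

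*Combined protocol and SAP*

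**What the plan says.** Abnormal laboratory findings are a secondary safety endpoint in protocol 1.2.2. Protocol 10.6.2 says that "the number of patients who experience abnormalities in clinical laboratory evaluations will be summarized by treatment group".

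SAP 3.4.3 defines such counts for ALT/AST ("For ALT and AST, the number and percent of subjects falling in each of the following categories based on the confirmed results", above 3 and above 5 times ULN) and for platelets (100,000 to below 140,000/mm³, and below 100,000/mm³). It defines none for any other analyte. For the rest it says: "Results from chemistry, hematology, complements, and coagulation panels as well as the change and percent change from baseline will be summarized" by group and visit. Potassium and creatinine are in the chemistry panel of protocol Appendix B. Urinalysis is a separate panel there and is not among those summarized, so urine protein goes to listings only.

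SAP 3.1.1 governs what enters the by-visit tables. On repeats: "Multiple results with the same visit label will be averaged". Results labelled unscheduled "will not be included in the by-visit summary tables and figures". The same sentence gives them another destination, saying that they "will be included in determining baseline, and in the laboratory abnormality summaries and shift analyses".

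The protocol stops dosing permanently for:
- confirmed potassium above 5.6 mmol/L without a clear cause (8.6.4);
- a confirmed creatinine rise of at least 0.5 mg/dL, printed as 26.5 µmol/L, that is also at least 40% above baseline (8.6.2);
- dipstick protein 2+, confirmed on retest and by more than 1.0 g/24 h (8.6.2).

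**The concern.** The SAP sends unscheduled results to abnormality summaries, but for potassium, creatinine and urine protein it defines no such summary. Elsewhere it says openly when it drops protocol content (the per-protocol set in 3.1.2, the model-based analyses in 3.3). It says nothing of the kind here, so this reads as an omission.

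These analytes matter for this target. Protocol 2.5 names hyperkalemia among the possible results of lost ENaC function and says patients will be monitored for it. Protocol 8.5 requires a retest of any triggering result, in the treatment or post-treatment period. Under SAP 3.1.1 that retest is either left out of the by-visit tables or averaged with the result it was meant to confirm. A between-group difference in stop-level renal or potassium values might then have to be counted by hand from listings.

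**Working it through.** The plan states no figure to reproduce and gives no event rate. The check sets the texts side by side, with invented patient values to show the mechanism.

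**1. Where a stop-level value appears under the SAP**

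| Result | Patient count | By-visit statistics | Listing |
|---|---|---|---|
| Potassium or central creatinine, scheduled, no repeat under the same label | no | yes, can show as the maximum | yes |
| The same, averaged with repeats | no | only as the average | yes |
| The same, labelled unscheduled | no | no | yes |
| Dipstick protein, any visit | no | no | yes |

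Local potassium results enter the summaries. Local creatinine results are only listed (SAP 3.1.1).

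**2. Averaging (assumed potassium values, one visit label)**

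- Trigger 5.8, confirming retest 5.7, recovery 5.0: (5.8 + 5.7 + 5.0)/3 = 5.5 mmol/L, below 5.6, so even the visit maximum need not show the event.
- 5.9 with a repeat of 5.0: (5.9 + 5.0)/2 = 5.45, hidden.
- 5.9 with a repeat of 5.7: (5.9 + 5.7)/2 = 5.8, still visible.

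**3. Creatinine change table against the stopping rule (assumed values)**

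The SAP baseline: "Baseline for other assessments is defined as the last non-missing measurement prior to the first Study Drug administration". The only renal baseline in protocol 8.6, the section to which 8.6.2 refers, is the average of Screening and Day 1. Take Screening 0.8, Day 1 1.0 and a later 1.45 mg/dL.

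- Protocol 8.6: (0.8 + 1.0)/2 = 0.9; 1.45 − 0.9 = 0.55, and 0.55/0.9 = 61%. Both conditions are met.
- SAP: 1.45 − 1.0 = 0.45, or 45%. This misses the 0.5 mg/dL condition.

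The rule also needs both conditions in one patient, which separate maxima of change and percent change cannot show.

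**4. The creatinine unit in protocol 8.6.2 (assumption: 1 mg/dL = 88.4 µmol/L)**

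0.5 × 88.4 = 44.2 µmol/L, and 26.5/88.4 = 0.30 mg/dL. For baseline b, the stop level is max(b + 0.5, 1.4b) on the mg/dL reading and max(b + 0.30, 1.4b) on the µmol/L reading.

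| Baseline (mg/dL) | Stop level, mg/dL reading | Stop level, µmol/L reading |
|---|---|---|
| 0.6 | 1.10 | 0.90 |
| 0.8 | 1.30 | 1.12 |
| 1.0 | 1.50 | 1.40 |
| 1.2 | 1.70 | 1.68 |
| 1.3 | 1.82 | 1.82 |

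The two readings agree from b = 0.5/0.4 = 1.25 mg/dL upward.

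**The case against.** Most stop-level values would be seen somewhere. Every result is listed. By-visit statistics include the maximum (SAP 3.1.1), and chemistry is scheduled through treatment, at Day 92 and at Day 162. If retests are labelled unscheduled, a scheduled 5.8 mmol/L stands alone as the visit maximum. The documents do not say how repeats are labelled, so the three-value average is a possibility and not an expectation. A laboratory change that alters treatment is an adverse event (protocol 9.3.1), so on-treatment stops should reach the AE tables and the reasons for terminating treatment. Appendix D grades potassium of 5.5 mmol/L or more as severe, so a reported case would show in the severity table. All of this stands and makes the point minor.

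It does not close the gap. Once dosing has ended there is no dose to stop, and a value judged not clinically significant is not to be reported as an AE (protocol 9.5.1). AE severity is also a poor stand-in for creatinine: the lowest Appendix D band starts at 1.5 mg/dL, above the stop level for baselines below 1.0 mg/dL on the mg/dL reading.

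Protocol 10.6.2 names no analyte or cut-off, and the SAP does not use the stop levels even where it counts (it has no row for ALT/AST above 8 times ULN or platelets below 75,000/mm³). The stop levels are therefore a sensible choice of cut-off, not one that the protocol dictates.

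A reader might infer from step 3 that the SAP baseline for creatinine is wrong. It is not. Protocol 10.4 sets the last pre-dose value as the analysis baseline for everything but liver chemistry, and 8.6 allows a different one for stopping rules.

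**Conclusion.** The point holds as a minor one. Potassium and creatinine have no patient count, and urine protein has no summary of any kind, although the protocol promises abnormality counts and the SAP routes unscheduled results to them. A potassium or creatinine value at a stop level escapes every laboratory table when it is unscheduled or averaged down, and escapes the AE tables too when it is not reported as an AE. The different baseline only means that the by-visit change table cannot replace a creatinine count.

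A reader might infer that stop-level events are lost or concealed. The documents do not support that: the listings are complete, scheduled unaveraged values show as maxima, and a hand count across 59 dosed patients is feasible. How many values are affected cannot be estimated, because no event rate or labelling rule for repeats is given.

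The unit conflict in 8.6.2 is a separate and definite error. It rests only on the conversion factor, and it moves the stop level by 0.18 mg/dL (1.30 against 1.12) at a baseline of 0.8. With treatment terminated it no longer affects dosing, but it decides who is counted.

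**What to change.** Add one table to SAP 3.4.3, by treatment group, over the treatment and post-treatment periods. Use individual results, not same-label averages, and include unscheduled values and, as SAP 3.1.1 already provides, local potassium. Rows:

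- potassium above 5.6 mmol/L;
- creatinine meeting both 8.6.2 conditions against the Screening/Day 1 average;
- dipstick protein 2+ or more, showing more than 1.0 g/24 h where measured.

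Use three columns: retest-confirmed, retested and not confirmed, and not retested. State the retest window, for example the 7 days already in 3.4.3. Do not carry over that section's rule "If there is no retest within 7 days, then the initial value is presumed confirmed", because 8.6.2 and 8.6.4 require confirmation. Title the table as thresholds met, not adjudicated stops.

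First correct protocol 8.6.2: state whether 0.5 mg/dL (about 44.2 µmol/L) or 26.5 µmol/L (about 0.30 mg/dL) governs, and put that value in the table footnote.

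The cost is one table from data already collected and one documented decision on the unit. No new sampling or adjudication is needed. The 24-hour protein measurement is not an Appendix B analyte, so it will exist for some patients only.
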